6.17.2 Laboratory Data

Laboratory data at Day -1 was analyzed by both a local laboratory and Worldwide Clinical Trials laboratory. Data from both laboratories will be listed but summary tables will only include data provided by Worldwide Clinical Trials.

All laboratory data will be listed and summarized using the International System of Units (SI). For continuous variables descriptive statistics of the observed values and change from baseline will be presented by cohort at each scheduled assessment and Early Termination (if applicable) for each hematology, serum chemistry, urinalysis, and coagulation parameter. For categorical variables the number and percentage of subjects in each reported level will be presented. Each hematology, serum chemistry, and urinalysis measurement will be classed as below, within, or above normal range, based on ranges supplied by the laboratory used. Shift tables in relation to the normal range from baseline to each post baseline assessment and Early Termination (if applicable) will be presented.

A listing of any markedly abnormal laboratory measurements (defined as meeting the criteria for grade 2 or higher in the sponsors grading of laboratory values presented in Appendix 1 to the study protocol) that were recorded throughout the study will be presented. The incidence of markedly abnormal laboratory results over the course of the study will be listed.

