9.5.2.2 Total Volume of Blood Sampling

Table 6 presents the number of blood samples and the total volume of blood that will be collected throughout the study. Additional samples may be taken at the discretion of the investigator if the results of any tests fall outside reference ranges or clinical symptoms necessitate testing to ensure subject safety.

Table 6	Summary of Blood Sample Volumes
---------	---------------------------------

	Sample Volume per Collection (mL)	Number of Collection Time Points	Total Volume Collected (mL)
Clinical laboratory tests	8.5	Screening (including pregnancy testing): 1 Baseline (Day -1): 1 Day 2: 1 Day 14 or early termination: 1	8.5×4=34
Viral test	8.5	Screening: 1	8.5×1=8.5
PK blood sampling	4	20	4×20=80
Blood sampling for plasma protein binding	12	2	2×12=24
Total			146.5

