9.7.1.8.3 LABORATORY VALUES

Laboratory results will be summarized using Système International (SI) units, as appropriate. For all quantitative parameters listed in Section 9.5.1.5.3, the actual value and the change from baseline to each postbaseline visit and to the end of treatment (defined as the last on-treatment value) will be summarized by visit and group using descriptive statistics. Qualitative parameters listed in Section 9.5.1.5.3 will be summarized using frequencies (number and percentage of subjects), and changes from baseline to each postbaseline visit and to end of treatment will be reported using shift tables. Percentages will be based on the number of subjects with both nonmissing baseline and relevant postbaseline results.

Laboratory test results will be assigned a low/normal/high (LNH) classification according to whether the value was below (L), within (N), or above (H) the laboratory parameter's reference range. Within-group comparisons for each laboratory parameter will be based on 3-by-3 tables (shift tables) that compare the baseline LNH classification to the LNH classification at each postbaseline visit and at the end of treatment.

Clinical laboratory results post baseline will be evaluated for markedly abnormal values.

Appendix 1 presents the Sponsor's grading for laboratory values that will be used to identify subjects with markedly abnormal laboratory values.

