14.3.4.4.1.1	Summary Statistics for the Change from Baseline in Coagulation at each
	Follow-up Assessment
	Safety Analysis Set
14.3.4.4.2.1	Listing of Markedly Abnormal Laboratory Results
	Safety Analysis Set
14.3.4.5.2.1	Summary Statistics for the Change from Baseline in Vital Signs at each

Follow-up Assessment Safety Analysis Set

14.3.4.6.2.1 Change from Baseline in the ECG Interpretation at each Follow-up Assessment Safety Analysis Set

Figure	Figure Title
Number	
14.2	PK Analysis
14.2.2.1	Mean Lemborexant and Metabolites Concentration-Time Profiles after Administration of Lemborexant 10 mg to Subjects with Mild Hepatic Impairment (Cohort A), Moderate Hepatic Impairment (Cohort B), or Normal Hepatic Function (Cohort C) on Linear and Semi-Logarithmic Scales PK Analysis Set
14.2.2.2	Lemborexant and Metabolites Concentration-Time Profiles for All Subjects after Administration of Lemborexant 10 mg to Subjects with Mild Hepatic Impairment (Cohort A) on Linear and Semi-Logarithmic Scales Safety Analysis Set
14.2.2.3	Lemborexant and Metabolites Concentration-Time Profiles for All Subjects after Administration of Lemborexant 10 mg to Subjects with Moderate Hepatic Impairment (Cohort B) on Linear and Semi-Logarithmic Scales Safety Analysis Set
14.2.2.4	Lemborexant and Metabolites Concentration-Time Profiles for All Subjects after Administration of Lemborexant 10 mg to Subjects with Normal Hepatic Function (Cohort C) on Linear and Semi-Logarithmic Scales Safety Analysis Set
14.2.2.5	Concentration-Time Profiles after Administration of Lemborexant and Metabolites with Linear Regression for Estimating the Terminal Elimination Rate Safety Analysis Set
14.2.2.6	Box Plot Comparing Lemborexant and Metabolites C _{max} Values after Administration of Lemborexant 10 mg to Subjects with Mild Hepatic Impairment (Cohort A), Moderate Hepatic Impairment (Cohort B), or Normal Hepatic Function (Cohort C) PK Analysis Set
14.2.2.7	Box Plot Comparing Lemborexant and Metabolites AUC ₍₀₋₇₂) Values after Administration of Lemborexant 10 mg to Subjects with Mild Hepatic Impairment (Cohort A), Moderate Hepatic Impairment (Cohort B), or Normal Hepatic Function (Cohort C) PK Analysis Set
14.2.2.8	Box Plot Comparing Lemborexant and Metabolites AUC _(0-t) Values after Administration of Lemborexant 10 mg to Subjects with Mild Hepatic Impairment (Cohort A), Moderate Hepatic Impairment (Cohort B), or Normal Hepatic Function (Cohort C) PK Analysis Set

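### The SAP's markedly abnormal laboratory listing covers pre-dose values and shows no baseline grade, and coagulation has no shift table; both depart from the protocol without being declared

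*SAP*

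**What the plan says.** On the flag, protocol section 9.7.1.8.3 (Laboratory Values) says: "Clinical laboratory results post baseline will be evaluated for markedly abnormal values". It points to Appendix 1 for the grades and sets no condition of worsening from baseline.

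SAP section 6.17.2 (Laboratory Data) fixes the threshold, "defined as meeting the criteria for grade 2 or higher in the sponsors grading of laboratory values", but not the protocol's window. The listing is of measurements "recorded throughout the study will be presented". It adds: "The incidence of markedly abnormal laboratory results over the course of the study will be listed". SAP section 12 has one matching output, 14.3.4.4.2.1, titled "Listing of Markedly Abnormal Laboratory Results".

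On shift tables, the protocol says: "Within-group comparisons for each laboratory parameter will be based on" 3-by-3 low/normal/high tables. The SAP says: "Each hematology, serum chemistry, and urinalysis measurement will be classed as below, within, or above normal range". Coagulation is not named there.

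SAP section 9 records no changes to the protocol's planned analysis, and the post-lock addendum does not touch section 6.17.2.

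**The concern.** Two cohorts are enrolled because of liver disease, and three of the five Child-Pugh items are laboratory tests. A flag that ignores both timing and baseline will pick up the disease that brought the subject into the study. Cohort C is screened the other way: exclusion 33 treats an abnormal liver function test as an indication of active liver disease. Anyone who counts liver-test flags by cohort from the listing will partly be counting the entry criteria.

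The SAP's other safety rules do refer to baseline. A TEAE must emerge, re-emerge or worsen (section 6.17.1), and blood pressure flags are changes relative to baseline (section 6.17.3).

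The low/normal/high shift tables do not fill the gap. A subject who is already high stays high however far the value rises. For PT, aPTT and INR there is no shift table at all. At stake is how readily the report lets a reader separate on-study worsening from pre-existing disease in impaired subjects, whose safety and tolerability is a stated secondary objective.

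**Working it through.** The plan states no figure on this point, so there is none to reproduce. The check compares windows, grade bands and planned outputs.

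1. **Window.** Protocol Table 6 schedules clinical laboratory draws at Screening and then "Baseline (Day -1): 1 Day 2: 1 Day 14 or early termination: 1". That is 4 time points, of which 2 (Screening and Day -1) precede dosing. The protocol's rule covers the last 2; the SAP's wording covers all 4. SAP section 6.1.1 counts a subject as enrolled from consent, which is given at Screening, so nothing in the SAP narrows the window.

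2. **Grade bands against entry bands** (protocol Appendix 1 and Table 1).
   - Albumin: grade 2 starts below 3 g/dL. A Child-Pugh score of 3 (below 2.8 g/dL) is therefore always grade 2 or higher. Within the 2-point band (2.8 to 3.5 g/dL), values from 2.8 to just under 3.0 g/dL also qualify. No assumption is needed.
   - Bilirubin: grade 2 is above 1.5 and up to 3.0 × ULN. The documents give no ULN. The 2-point band starts at 2 mg/dL, so all of it is grade 2 or higher when 1.5 × ULN < 2, that is, ULN < 2/1.5 = 1.33 mg/dL. At an assumed ULN of 1.0 to 1.3, grade 2 starts above 1.5 to 1.95 mg/dL. At 1.4 to 1.5 it starts above 2.1 to 2.25 mg/dL, and the overlap is only partial.

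3. **What each rule does.** Illustrative bilirubin pairs in mg/dL, assumed ULN 1.2 (grade 2 above 1.8, grade 3 above 3.6):

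| Baseline → post-dose | Grade | Low/normal/high shift | SAP, any time | Protocol, post-baseline | Grade ≥2 and worse than baseline |
|---|---|---|---|---|---|
| 2.5 → 2.5 | 2 → 2 | H → H | flagged | flagged | no |
| 2.5 → 1.7 | 2 → 1 | H → H | flagged | no | no |
| 2.5 → 4.0 | 2 → 3 | H → H | flagged | flagged | flagged |
| 1.0 → 2.0 | 0 → 2 | N → H | flagged | flagged | flagged |
| 2.5 → 3.5 | 2 → 2 | H → H | flagged | flagged | no |

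   The improving subject (row 2) is listed only under the SAP's window. The subject moving from grade 2 to grade 3 (row 3) does not change cell in the shift table. The within-grade rise (row 5) is missed by a rule that requires a worse grade, so such a rule cannot stand alone.

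4. **How many pre-existing flags.** The share of Cohort B with a grade 2 value before dosing is not given; call it p. The expected number among 8 subjects is 8p, and the chance of at least one is 1 − (1 − p)^8.
   - p = 0.125: 1 subject; 1 − 0.875^8 = 0.66
   - p = 0.25: 2 subjects; 1 − 0.75^8 = 0.90
   - p = 0.50: 4 subjects; 1 − 0.5^8 = 0.996

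5. **Coagulation.** Protocol Table 3 includes PT, aPTT and INR among the laboratory tests. SAP section 12 plans normal-range shift tables for hematology (14.3.4.1.2.1), chemistry (14.3.4.2.2.1) and urinalysis (14.3.4.3.2.1). For coagulation it plans only the change-from-baseline summary (14.3.4.4.1.1). Appendix 1 has no grade for PT, aPTT or INR, so these tests cannot be flagged as markedly abnormal either.

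**The case against.** A reader might infer three stronger things, and the documents support none of them.

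- **That real worsening is hidden.** It is not. Section 6.17.2 lists all laboratory data and summarises change from baseline by cohort and assessment, coagulation included. Section 6.3 puts minimum and maximum in those summaries, so with 8 subjects the largest scheduled rise is visible. Protocol section 9.5.1.5.1 makes a laboratory abnormality that leads to intervention an adverse event.
- **That Cohort B entry guarantees grade 2 values.** Class B needs 7 points. Mild or moderate ascites (2) and grade 1 or 2 encephalopathy (2), with 1 point each for albumin, bilirubin and PT, give 1+1+1+2+2 = 7. Albumin of 3.0 to 3.5 g/dL scores 2 points without reaching grade 2. Overlap is plausible, not certain.
- **That a between-cohort incidence table will mirror enrolment.** No such table is planned. The flag feeds a listing, and the incidence is also to be listed.

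It can also be said that the listing is sorted by cohort, subject, parameter and day, so a flagged pre-dose value sits beside the same subject's flagged post-dose value. That holds when both values qualify. When only one does, the listing does not show the other or its grade.

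Finally, the protocol has no worsening condition, so its absence from the SAP is not a departure. That is correct. The departures are the wider window and the missing coagulation shifts; showing grade change is an improvement on both documents.

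**Conclusion.** The point holds in a limited form. The SAP departs from the protocol in two undeclared ways: the markedly abnormal flag covers pre-dose values, and coagulation has no normal-range shift table. Because grade 2 bands overlap Child-Pugh entry values, the listing can be expected to mix pre-existing cirrhosis abnormalities with post-dose ones, and no planned output separates them by grade.

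The albumin overlap rests on the documents alone. The bilirubin overlap covers the whole 2-point band if the ULN is below 1.33 mg/dL, which is an assumption. The figure of 1 to 4 pre-existing flags in Cohort B rests on an assumed share of 12.5% to 50%.

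The impact is modest: descriptive output for a secondary safety objective, a single dose, 24 subjects and two scheduled post-dose laboratory draws. No PK estimate is affected.

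**What to change.** - In SAP section 6.17.2, restrict the markedly abnormal flag to post-baseline values, as the protocol does, and show the baseline grade (baseline as defined in section 6.2.4) beside each flagged value.
- Add a table by cohort of baseline grade against worst post-baseline grade for the tests graded in Appendix 1. State whether unscheduled repeats count towards the worst value, since section 6.2.7 otherwise disregards them.
- Add low/normal/high shift tables for PT, aPTT and INR. A grade-based table cannot cover them.
- Keep the change-from-baseline summaries. A grade rule misses within-grade rises such as 2.5 to 3.5 mg/dL, and coagulation has no grades.
- If the sponsor prefers the present window and outputs, declare both differences in section 9.

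The cost is SAP wording and minor programming on data already collected. The addendum shows that the database is locked, but SAP section 6 allows additional tables if the clinical study report justifies them. The one loss is that purely pre-dose abnormalities leave the markedly abnormal listing; they remain in the full laboratory listings and in the baseline margin of the new table.

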6.17.3 Vital Signs

Descriptive statistics of the observed values and change from baseline will be presented by cohort and timepoint for the following:

- Systolic blood pressure (mmHg)
- Diastolic blood pressure (mmHg)
- Pulse rate (bpm)
- Respiration Rate (breaths/min)
- Body Temperature (degrees Celsius)

The incidence of subjects reporting an increase or decrease greater than 20mmHg in systolic or 15 mmHg in diastolic blood pressure relative to baseline will be summarized at each post baseline assessment.

Weight at Day -1 will be listed only.

6.17.4 Electrocardiogram Data

Shift tables in relation to the overall interpretation (Normal, Abnormal Not Clinically Significant [NCS], and Abnormal Clinically Significant [CS]) from baseline to each post baseline assessment will be presented by cohort and overall.

6.17.5 Physical Examination

Significant findings at the Screening physical examination will be recorded on the Medical History and Current Medical Conditions CRF page and changes from screening physical examination findings that meet the definition of an AE will be recorded on the Adverse Events CRF, this data will be listed as described in the previous sections.

7 INTERIM ANALYSIS

No interim analyses are planned.

8 DATA SAFETY MONITORING BOARD ANALYSIS

There is no data safety monitoring board (DSMB) for this study.

9 CHANGES TO PLANNED PROTOCOL ANALYSIS

None.

10 DEFINITIONS AND CONVENTIONS FOR DATA HANDLING

10.1 Pharmacokinetic Data Handling

10.1.1 Lower Limit of Quantification of Plasma Concentration

The LLOQ for lemborexant and its metabolites (M4, M9, and M10) is 0.0500 ng/mL in plasma

12 LIST OF TABLES, FIGURES AND LISTINGS

Please note: Table, Listing, and Figure titles are subject to change upon final analysis. Tables, Listings, and Figures may be consolidated as necessary.

Table	Table Title
Number	Subject Disposition
14.1.1	Subject Disposition
14.1.1.1	Enrolled Subjects
14112	Saraaning Eailuras
14.1.1.2	Demography Descline Characteristics Treatment Compliance and
14.1.3	Analysis Populations
14131	Datasets Analyzed
14.1.3.1	Enrolled Subjects
1/1/1/1	Demography and Baseline Characteristics
17.1.7.1.1	Safety Analysis Set
14 2	PK Analysis
14.2.2.1	Descriptive Statistics for Lemborexant and Metabolites Concentration-Time Data after Administration of Lemborexant 10 mg to Subjects with Mild Hepatic Impairment (Cohort A), Moderate Hepatic Impairment (Cohort B), or Normal Hepatic Function (Cohort C)
	PK Analysis Set
14.2.2.2	Descriptive Statistics for Percent Bound and Unbound of Lemborexant and Metabolites in Plasma after Administration of Lemborexant 10 mg to Subjects with Mild Hepatic Impairment (Cohort A), Moderate Hepatic Impairment (Cohort B), or Normal Hepatic Function (Cohort C) PK Analysis Set
14231	Descriptive Statistics for Pharmacokinetic Parameters of Lemborexant after
	Administration of Lemborexant 10 mg to Subjects with Mild Hepatic Impairment (Cohort A), Moderate Hepatic Impairment (Cohort B), or Normal Hepatic Function (Cohort C) PK Analysis Set
14.2.3.2	Descriptive Statistics for Pharmacokinetic Parameters of M4 after Administration of Lemborexant 10 mg to Subjects with Mild Hepatic Impairment (Cohort A), Moderate Hepatic Impairment (Cohort B), or Normal Hepatic Function (Cohort C) PK Analysis Set
14.2.3.3	Descriptive Statistics for Pharmacokinetic Parameters of M9 after Administration of Lemborexant 10 mg to Subjects with Mild Hepatic

	Impairment (Cohort A), Moderate Hepatic Impairment (Cohort B), or Normal Hepatic Function (Cohort C)
	PK Analysis Set
14.2.3.4	Descriptive Statistics for Pharmacokinetic Parameters of M10 after Administration of Lemborexant 10 mg to Subjects with Mild Hepatic Impairment (Cohort A), Moderate Hepatic Impairment (Cohort B), or Normal Hepatic Function (Cohort C) PK Analysis Set
14.2.4.1	Statistical Analysis of the Natural Log-Transformed Systemic Exposure Parameters of Lemborexant (Mild or Moderate Hepatic Impairment vs. Normal Hepatic Function) PK Analysis Set
14.2.4.2	Statistical Analysis of the Natural Log-Transformed Systemic Exposure Parameters of M4 (Mild or Moderate Hepatic Impairment vs. Normal Hepatic Function) PK Analysis Set
14.2.4.3	Statistical Analysis of the Natural Log-Transformed Systemic Exposure Parameters of M9 (Mild or Moderate Hepatic Impairment vs. Normal Hepatic Function) PK Analysis Set
14.2.4.4	Statistical Analysis of the Natural Log-Transformed Systemic Exposure Parameters of M10 (Mild or Moderate Hepatic Impairment vs. Normal Hepatic Function) PK Analysis Set
14.3.1	Safety - AEs
14.3.1.2.1	Summary of Treatment-Emergent Adverse Event Reporting Safety Analysis Set
14.3.1.3.1	MedDRA Summary of Treatment-Emergent Adverse Events by Primary System Organ Class and Preferred Term Safety Analysis Set
14.3.1.3.2	Serious Adverse Events and Deaths by Primary System Organ Class and Preferred Term Safety Analysis Set
14.3.1.4.1	MedDRA Summary of Treatment-Emergent Adverse Events by Primary System Organ Class, Preferred Term, and Severity Safety Analysis Set
14.3.1.5.1	MedDRA Summary of Treatment-Emergent Treatment-related Adverse Events by Primary System Organ Class and Preferred Term Safety Analysis Set

14.3.1.6.1	Treatment-Emergent Non-serious Adverse Events by Primary System Organ
	Class and Preferred Term
	Safety Analysis Set
14.3.2	Safety – Other AEs
14.3.2.1.1	Listing of Deaths
	Safety Analysis Set
14.3.2.2.1	Listing of Serious Adverse EventsSafety Analysis Set
14.3.2.3.1	Listing of Adverse Events Leading to Study Drug Discontinuation
	Safety Analysis Set
14.3.2.4.1	Listing of Potential Cataplexy Adverse Events
	Safety Analysis Set
14.3.2.4.2	Listing of Supplemental Information Questionnaire for Potential Cataplexy
	Adverse Events
	Safety Analysis Set
14.3.4	Safety - Other
14.3.4.1.1.1	Summary Statistics for the Change from Baseline in Hematology at each
	Follow-up Assessment
	Safety Analysis Set
14.3.4.1.2.1	Normal Range Shifts in Hematology from Baseline to each Follow-up
	Assessment
	Safety Analysis Set
14.3.4.2.1.1	Summary Statistics for the Change from Baseline in Chemistry at each
	Follow-up Assessment
	Safety Analysis Set
14.3.4.2.2.1	Normal Range Shifts in Chemistry from Baseline to each Follow-up
	Assessment
	Safety Analysis Set
14.3.4.3.1.1	Summary Statistics for the Change from Baseline in Urinalysis at each Follow-up Assessment
	Safety Analysis Set
14.3.4.3.2.1	Normal Range Shifts in Urinalysis from Baseline to each Follow-up
	Assessment
	Safety Analysis Set
14.3.4.4.1.1	Summary Statistics for the Change from Baseline in Coagulation at each
	Follow-up Assessment
	Safety Analysis Set
14.3.4.4.2.1	Listing of Markedly Abnormal Laboratory Results
	Safety Analysis Set
14.3.4.5.2.1	Summary Statistics for the Change from Baseline in Vital Signs at each

Follow-up Assessment Safety Analysis Set

14.3.4.6.2.1 Change from Baseline in the ECG Interpretation at each Follow-up Assessment Safety Analysis Set

Figure	Figure Title
Number	
14.2	PK Analysis
14.2.2.1	Mean Lemborexant and Metabolites Concentration-Time Profiles after Administration of Lemborexant 10 mg to Subjects with Mild Hepatic Impairment (Cohort A), Moderate Hepatic Impairment (Cohort B), or Normal Hepatic Function (Cohort C) on Linear and Semi-Logarithmic Scales PK Analysis Set
14.2.2.2	Lemborexant and Metabolites Concentration-Time Profiles for All Subjects after Administration of Lemborexant 10 mg to Subjects with Mild Hepatic Impairment (Cohort A) on Linear and Semi-Logarithmic Scales Safety Analysis Set
14.2.2.3	Lemborexant and Metabolites Concentration-Time Profiles for All Subjects after Administration of Lemborexant 10 mg to Subjects with Moderate Hepatic Impairment (Cohort B) on Linear and Semi-Logarithmic Scales Safety Analysis Set
14.2.2.4	Lemborexant and Metabolites Concentration-Time Profiles for All Subjects after Administration of Lemborexant 10 mg to Subjects with Normal Hepatic Function (Cohort C) on Linear and Semi-Logarithmic Scales Safety Analysis Set
14.2.2.5	Concentration-Time Profiles after Administration of Lemborexant and Metabolites with Linear Regression for Estimating the Terminal Elimination Rate Safety Analysis Set
14.2.2.6	Box Plot Comparing Lemborexant and Metabolites C _{max} Values after Administration of Lemborexant 10 mg to Subjects with Mild Hepatic Impairment (Cohort A), Moderate Hepatic Impairment (Cohort B), or Normal Hepatic Function (Cohort C) PK Analysis Set
14.2.2.7	Box Plot Comparing Lemborexant and Metabolites AUC ₍₀₋₇₂) Values after Administration of Lemborexant 10 mg to Subjects with Mild Hepatic Impairment (Cohort A), Moderate Hepatic Impairment (Cohort B), or Normal Hepatic Function (Cohort C) PK Analysis Set
14.2.2.8	Box Plot Comparing Lemborexant and Metabolites AUC _(0-t) Values after Administration of Lemborexant 10 mg to Subjects with Mild Hepatic Impairment (Cohort A), Moderate Hepatic Impairment (Cohort B), or Normal Hepatic Function (Cohort C) PK Analysis Set

14.2.2.9	Box Plot Comparing Lemborexant and Metabolites AUC _(0-inf) Values after Administration of Lemborexant 10 mg to Subjects with Mild Hepatic Impairment (Cohort A), Moderate Hepatic Impairment (Cohort B), or Normal Hepatic Function (Cohort C)
	PK Analysis Set
14.2.2.10	Scatterplot and Regression Analysis for Pharmacokinetic Parameters of Lemborexant and Metabolites versus Child-Pugh Score at Screening PK Analysis Set
14.2.2.11	Scatterplot and Regression Analysis for Pharmacokinetic Parameters of Lemborexant and Metabolites versus MELD Score at Screening PK Analysis Set
14.2.2.12	Scatterplot and Regression Analysis for Pharmacokinetic Parameters of Lemborexant and Metabolites versus Serum Albumin at Screening PK Analysis Set
14.2.2.13	Scatterplot and Regression Analysis for Pharmacokinetic Parameters of Lemborexant and Metabolites versus Total Bilirubin at Screening PK Analysis Set
14.2.2.14	Scatterplot and Regression Analysis for Pharmacokinetic Parameters of Lemborexant and Metabolites versus Prothrombin Time at Screening PK Analysis Set
14.2.2.15	Scatterplot and Regression Analysis for Pharmacokinetic Parameters of Lemborexant and Metabolites versus Creatinine at Screening PK Analysis Set
14.2.2.16	Scatterplot and Regression Analysis for Pharmacokinetic Parameters of Lemborexant and Metabolites versus ALT at Screening PK Analysis Set
14.2.2.17	Scatterplot and Regression Analysis for Pharmacokinetic Parameters of Lemborexant and Metabolites versus AST at Screening PK Analysis Set

Listing Number	Listing Title
16.2.1	Subject Disposition
16.2.1.1	Subjects Disposition
	Enrolled Subjects
16.2.2	Protocol Deviations
16.2.2.1	Protocol Deviations
	Safety Analysis Set
16.2.2.2	Inclusion/Exclusion Not Met
16.2.3	Demography, Baseline Characteristics, Treatment Compliance, and
	Analysis Populations
16.2.3.1	Analysis Populations
	Enrolled Subjects
16.2.4.1	Demographics
	Enrolled Subjects
16.2.4.2	Child Pugh Classification
	Safety Analysis Set
16.2.4.3	Previous Medical History
	Safety Analysis Set
16.2.4.4	Ongoing Medical History
	Safety Analysis Set
16.2.4.5	Prior Medications
	Safety Analysis Set
16.2.4.6	Concomitant Medications
	Safety Analysis Set
16.2.5.1	Dosing Information
	Safety Analysis Set
16.2.6	РК
16.2.6.1	Lemborexant and Metabolites Concentration-Time and Protein Binding Data
	Listing by Subject
	Safety Analysis Set
16.2.6.2	Lemborexant Pharmacokinetic Parameter Listing by Subject
	PK Analysis Set
16.2.6.3	M4, M9, and M10 Pharmacokinetic Parameter Listing by Subject
	PK Analysis Set
16.2.6.4	Terminal Elimination Rate of Lemborexant and Metabolites
	for Individual Subjects after Administration of Lemborexant 10 mg to
	Subjects with Mild Hepatic Impairment (Conort A), Moderate Hepatic

Eisai, Inc. E2006-A001-104 Statistical Analysis Plan Version 1.0 Issue Date 11-MAY-2018

	Impairment (Cohort B), or Normal Hepatic Function (Cohort C)
	PK Analysis Set
16.2.6.5	PK Text Output
16.2.6.6	ANOVA SAS Output Text
16.2.7	Safety – AEs
16.2.7.1	Adverse Events
	Safety Analysis Set
16.2.8	Safety – Labs
16.2.8.1	Hematology
	Safety Analysis Set
16.2.8.2	Serum Chemistry
	Safety Analysis Set
16.2.8.3	Urinalysis
	Safety Analysis Set
16.2.8.4	Coagulation
	Safety Analysis Set
16.2.8.5	Viral Serology
	Safety Analysis Set
16.2.8.6	Drug and Alcohol Screen
	Safety Analysis Set
16.2.8.7	Pregnancy
	Safety Analysis Set
16.2.8	Safety – Other
16.2.8.8	Vital Signs Data
	Safety Analysis Set
16.2.8.9	ECG Data
	Safety Analysis Set
16.2.8.10	Height and Weight Data
	Safety Analysis Set

Eisai, Inc. E2006-A001-104 Post database lock SAP Addendum Version: 1.0 Issue Date: 24-JUL-2018

STATISTICAL ANALYSIS PLAN

POST DATABASE LOCK ADDENDUM

An Open-label, Parallel-Group Study to Evaluate the Pharmacokinetics of Lemborexant and its Metabolites in Subjects with Mild and Moderate Hepatic Impairment Compared to Healthy Subjects

Protocol Ref: E2006-A001-104

Version: 1.0

Date effective: 24-JUL-2018

Eisai, Inc. E2006-A001-104 Post database lock SAP Addendum Version: 1.0 Issue Date: 24-JUL-2018

SUMMARY OF SECTIONS

